2.3. Measurements

Before and after the completion of the 6-month workplace intervention program selected health and functional capacity indices will be assessed (Figure 1), using widely used, and reliable tests, that have showed high test-retest reliability (ICC = 0.95 - 0.98; SEM = 0.76 - 1.22; SEM% = 2.6 - 4) in office workers. Furthermore, the adherence to the Mediterranean diet was assessed before and after the 6-month time period using specific questionnaire.

[figure not shown]

Figure 1. Health, functional capacity and dietary habits measurements before and after the 6-month time period.

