2.5. Statistical Analysis

All statistical analyses will be performed using the IBM SPSS Statistics v.31 software (IBM Corporation, Armonk, New York, NY, USA), and the results will be presented as means \pm standard deviations. Before the commencement of the study, a power analysis, using software package GPower 3.1, for statistical test "ANOVA: Repeated measures, within-between interaction (2 groups and 2 measures)" and effect size 0.30 (a err prob = 0.05) was performed. The statistical power analysis indicated that a total sample of 32 participants (16 participants in each group) would yield adequate power (0.90). The normality of the data will be examined using the Shapiro-Wilk test. Two-way analyses of variances (2-way ANOVAs) [2 groups (IG and CG) \times 2-time points (pre- and post-intervention)] with repeated measures on the "time-point" factor and Sidak pairwise comparisons will be applied to locate the significantly different means within and between groups. Independent t-tests will be also used to compare the percentage change (from pre- to post-measurement) between the two groups (IG and CG). The magnitude of the difference between measurements and groups will be examined using Cohen's *d* effect sizes (ES). The level of significance for all statistical analyses will be set at $p < 0.05$.

References

1. American College of Sports Medicine (ACSM) ACSM's Guidelines for Exercise Testing and Prescription. 9th ed. Lippincott Williams & Wilkins; Philadelphia, PA, USA: 2013. pp. 40–107.

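### Cohen's d has no stated standardiser or single contrast, and the plan gives no confidence interval and no between-arm difference in the outcome's own units

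*Combined protocol and SAP*

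**What the plan says.** Section 2.5 is the whole analysis plan. On description it says that "the results will be presented as means" with standard deviations. On testing, it plans a two-group by two-time-point repeated-measures ANOVA, after which "Sidak pairwise comparisons will be applied to locate the significantly different means within and between groups". An independent t-test then compares percentage change from pre to post between IG and CG. On effect size, "The magnitude of the difference between measurements and groups will be examined using" Cohen's d.

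The section does not say which SD divides the difference in d, or which contrast (pre to post within an arm, arms at 6 months, or arms in change) is the effect of interest. It specifies no confidence interval for any quantity. It does not list the between-arm difference, or the difference in change, in mmHg, percent body fat or other natural units as an output.

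Section 1 sets the objective as evaluating the efficacy of the programme, and Section 2.4 describes a parallel randomised design with a control arm that receives no intervention.

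**The concern.** The comparison that randomisation protects is IG against CG. A d between measurements is computed inside one arm. It adds to any programme effect whatever else moves scores over six months: familiarity with the tests, season, and regression to the mean in people selected for BMI of at least 30 kg/m². The control arm exists to remove these.

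A d between groups taken from the 6-month means is a randomised comparison, but it carries part of whatever baseline difference chance has produced. With 16 to 20 people per arm that part is not small.

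Because the standardiser is open, the same data can yield different values of d, and the choice can be made after the results are known. Without an interval, a reader cannot tell how wide a range of true effects the data allow.

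**Working it through.** **Inputs from the document.** Section 2.5: 16 per arm (32 in total), power 0.90, α 0.05, and "effect size 0.30 (a err prob = 0.05) was performed", read here as Cohen's f. Section 2.1: 40 people expected, so up to 20 per arm under equal allocation. The 6-month pre-post correlation r and the control-arm change are not given; the values below are assumptions. Equal SDs at both time points and in both arms are also assumed.

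**1. The plan's own figure.** For the 2×2 within-between interaction, λ = f²·N·m/(1−r). With f = 0.30, N = 32, m = 2 and r = 0.5 (assumed), λ = 0.09 × 32 × 2/0.5 = 11.52 on 1 and 30 df, giving power 0.907. The smallest even N that reaches 0.90 is 32, so the stated N and power reproduce.

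**2. Choice of contrast.** Suppose IG changes by 0.6 SD. The within-IG d on the raw SD is 0.6 whatever CG does; the between-arm d is 0.6 minus the CG change.

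| CG change (SD) | Between-arm d | Within-IG d ÷ between-arm d |
|---|---|---|
| 0 | 0.6 | 1.0 |
| 0.2 | 0.4 | 1.5 |
| 0.3 | 0.3 | 2.0 |

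**3. Choice of standardiser.** SD of change = SD·√(2(1−r)), so d on the change SD divided by d on the raw SD is 1/√(2(1−r)).

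| r (assumed) | Factor |
|---|---|
| 0.3 | 0.85 |
| 0.5 | 1.0 |
| 0.8 | 1.6 |
| 0.9 | 2.2 |

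**4. Chance baseline difference in a post-test d.** The 95% range of the baseline difference at 16 per arm is ±1.96 × √(2/16) = ±0.69 SD. The part expected to carry into the 6-month difference is r times that: ±0.35 at r = 0.5 and ±0.55 at r = 0.8. At 20 per arm, 1.96 × √(2/20) = 0.62, giving ±0.31 and ±0.50.

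**5. Precision that would go unreported.** Exact 95% CIs for an unadjusted between-arm d, by inverting the noncentral t with 2n−2 df:

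| Observed d | 16 per arm | 20 per arm |
|---|---|---|
| 0.5 | −0.21 to 1.20 | −0.13 to 1.13 |
| 0.8 | 0.07 to 1.52 | 0.15 to 1.44 |

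**6. Can a reader recover the interval?** The variance of change is s₁² + s₂² − 2·r·s₁·s₂. Pre and post SDs supply s₁ and s₂ but not r. The point estimate of the difference in change follows by subtracting the reported means; its interval does not.

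**7. What baseline adjustment gains.** Ignoring the loss of one degree of freedom, the variance of the ANCOVA estimate is 1−r² times that of the post-test comparison and (1+r)/2 times that of the change comparison. At r = 0.5 both ratios are 0.75; at r = 0.8 they are 0.36 and 0.90.

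**The case against.** The plan is not confined to d. Means with SDs are in natural units, and the percentage-change t-test is a between-arm comparison of change. A reader can subtract means to get the difference in change. This stands, and it rules out saying that magnitude is reported only as Cohen's d. It does not supply the interval, and the percentage-change test is in percent, with no estimate or interval specified for it.

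A reader might infer that d could be inflated three- to five-fold, because Section 2.3 cites "high test-retest reliability (ICC = 0.95 - 0.98; SEM = 0.76 - 1.22; SEM% = 2.6 - 4) in office workers" and the step 3 factor is 3.2 at 0.95 and 5.0 at 0.98. The document does not support that. Those figures are test-retest reliability, not the 6-month pre-post correlation, which should be lower. At r = 0.5, the value that reproduces the plan's N, the factor is 1.0, and below 0.5 it is less than 1.

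A reader might also count the full ±0.69 SD baseline difference as error in a post-test d. Only r times it is expected to carry over, and under randomisation this is imprecision, not bias.

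Section 2.5 does not say that a within-arm d will be presented as the programme effect, or name any d as the headline. The problem is that nothing in it prevents this. Finally, the intervals in step 5 are for an unadjusted d; those for the adjusted difference proposed below would depend on r.

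**Conclusion.** The point holds as a defect in the planned effect estimate. Section 2.5 specifies no confidence interval, no between-arm difference in natural units, and neither a standardiser nor a single contrast for d. Followed as written, the plan yields a within-arm pre-post d and between-group comparisons not adjusted for the baseline value.

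The size is conditional. The contrast can double d if CG changes half as much as IG. The standardiser changes it by a factor of 0.85 to 2.2 for r from 0.3 to 0.9. Baseline carry-over at 16 per arm is about ±0.35 to ±0.55 for r from 0.5 to 0.8. These rest on assumed values of r and of control-arm change. The missing interval does not depend on either: at 16 per arm a between-arm d of 0.8 is compatible with anything from 0.07 to 1.52.

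A reader might infer that the sample size is undermined. It is not: N = 32 and power 0.90 concern the interaction test, which can stay as planned.

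**What to change.** Replace the Cohen's d sentence in Section 2.5 with text to this effect:

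- For each continuous outcome, the effect estimate is the IG–CG difference at 6 months adjusted for the baseline value of that outcome (ANCOVA), in the outcome's own units, with a 95% CI.
- If a standardised effect is wanted, it is that adjusted difference divided by the pooled baseline SD, with its 95% CI.
- Any within-arm d is labelled descriptive, with its standardiser stated, and is not presented as the effect of the programme.

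Under randomisation the adjusted difference and the difference in change estimate the same effect, so the target is unchanged and the planned ANOVA can remain. The cost is one extra model per outcome beside the 2×2 ANOVA and an added estimate-and-interval column in the tables. No new data are needed. Some effect sizes will look smaller or less certain than a within-arm d would.

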Official Title: A combined workplace intervention including exercise and nutrition for health promotion in obese office workers: a randomized controlled study

NCT number (if available): It's not yet available.

Date of the document: 16/5/2026

1. Objective

Therefore, the main objective of this study is to design, implement, guide and evaluate the efficacy of a 6-month daily supervised workplace (during the working hours) combined intervention program including exercise (flexibility, balance, strength, aerobic capacity) and nutrition on selected health (body fat and circumferences, blood pressure, respiratory function, lipidemic profile), b) functional capacity indices (flexibility, static and dynamic balance, handgrip strength and aerobic capacity) and c) dietary habits (adherence to the Mediterranean diet, daily water consumption amount) of obese office workers. Another important objective of this study is to investigate the individualized responses per participant following the 6-month workplace intervention program. This is of fundamental importance since the individual characteristics of the participants may affect the efficiency of the intervention program and the generalization of study results in the whole population.

2. Methods

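### No primary outcome is named and at least 12 outcomes are each tested at 0.05 with no control across them, giving roughly a 23–46% chance of at least one false-positive interaction if the programme has no effect

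*Combined protocol and SAP*

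**What the plan says.** Section 1 (Objective) gives one main aim: "the main objective of this study is to design, implement, guide and evaluate the efficacy of a 6-month daily supervised workplace" programme. The outcomes under that aim fall into three groups:

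- "health (body fat and circumferences, blood pressure, respiratory function, lipidemic profile")
- "functional capacity indices (flexibility, static and dynamic balance, handgrip strength and aerobic capacity")
- "dietary habits (adherence to the Mediterranean diet, daily water consumption amount")

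No outcome is called primary or secondary. The further objective on individual responses does not rank them either, and sections 2.3 and 2.4 repeat the same groups without priority.

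Section 2.5 (Statistical Analysis) plans a 2 × 2 repeated-measures ANOVA (group by time), after which "Sidak pairwise comparisons will be applied to locate the significantly different means within and between groups". It adds independent t-tests comparing percentage change between the groups. On the threshold it says: "The level of significance for all statistical analyses will be set at" p < 0.05. It gives no order of testing, no adjustment across outcomes and no rule for concluding that the programme works. The power analysis (within-between interaction, effect size 0.30, alpha 0.05, 32 participants, power 0.90) is attached to no outcome.

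**The concern.** A 5% significance level protects one pre-specified test. Here one efficacy question is put to a dozen or more outcomes, each with its own 5% chance of a false positive, and the plan does not say which of them answers the question. Whoever writes the report could give prominence to whichever outcome crosses the threshold, and nothing fixed in advance would show that this had happened. The error rate of the overall conclusion would then be well above 5%. Readers also could not tell which hypothesis the 0.90 power refers to. This cannot be put right credibly once the 6-month results have been seen.

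**Working it through.** **1. Counting outcomes (section 1).**
- Health: body fat, circumferences, blood pressure, respiratory function, lipid profile = 5.
- Functional capacity: flexibility, static balance, dynamic balance, handgrip strength, aerobic capacity = 5.
- Dietary: Mediterranean diet adherence, water consumption = 2.
- Total 5 + 5 + 2 = 12. This is a floor, because circumferences, blood pressure, respiratory function and lipids usually yield several variables each.

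**2. Reproducing the plan's own figure (section 2.5).** Inputs from the plan are f = 0.30, alpha = 0.05, 2 groups, m = 2 measures and N = 32. The pre-post correlation ρ is not stated; assume 0.5, with sphericity correction 1.
- λ = N·m·f²/(1 − ρ) = 32 × 2 × 0.09/0.5 = 11.52, with 1 and 30 degrees of freedom.
- Power = 0.907. N = 30 gives 0.887, so 32 is the smallest even N reaching 0.90.
- The required N depends on the assumption: 44 at ρ = 0.3 and 20 at ρ = 0.7.

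The stated sample size therefore reproduces, for one test of one outcome at 0.05.

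**3. Error rate with one interaction test per outcome and no true effect.**
- Independent outcomes: 1 − 0.95¹² = 0.460. The expected number of false positives is 12 × 0.05 = 0.6.
- Correlated outcomes (12 equicorrelated normal test statistics; the correlations are assumptions):

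| Inter-outcome correlation | Chance of at least one false positive |
|---|---|
| 0 | 0.46 |
| 0.3 | 0.40 |
| 0.5 | 0.32 |
| 0.7 | 0.23 |

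Simulating whole trials with 20 per arm gives nearly the same values: 0.45, 0.39, 0.33 and 0.24. With independent outcomes the chance passes one half at 14 variables: 1 − 0.95¹⁴ = 0.512.

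**4. Adding the other tests planned for each outcome.** Simulated with 12 outcomes, 20 per arm, no true effect, an assumed pre-post correlation of 0.5 and an assumed baseline coefficient of variation of 10%:

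| Significant result on any of | r = 0 | r = 0.3 | r = 0.5 | r = 0.7 |
|---|---|---|---|---|
| Interaction or percentage-change t-test | 0.48 | 0.42 | 0.35 | 0.25 |
| These, or post-intervention between-group comparison, or pre-post comparison in the intervention group | 0.79 | 0.73 | 0.64 | 0.50 |

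The percentage-change test adds little because it nearly duplicates the interaction. The pairwise comparisons add much more, if they are made within factor levels without effective adjustment.

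**5. What Sidak does.** The adjusted p-value for k comparisons is 1 − (1 − p)ᵏ. If comparisons are made within each level of the other factor, two levels leave one comparison, so k = 1 and the adjusted value equals p. If instead all four cell means were compared, there would be 4 × 3/2 = 6 comparisons and Sidak would adjust. Section 2.5 does not say which is meant. Under neither reading is it described as acting across outcomes.

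**6. The alternative of adjusting all 12 equally.** The Bonferroni level is 0.05/12 = 0.00417. Power per outcome at f = 0.30:

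| N | ρ = 0.3 | ρ = 0.5 | ρ = 0.7 |
|---|---|---|---|
| 32 (the plan's N) | 0.42 | 0.62 | 0.89 |
| 40 (volunteers expected before screening) | 0.57 | 0.77 | 0.96 |

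At ρ = 0.5, N = 52 would be needed for power 0.90.

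**The case against.** The best defence is that the plan never says one significant outcome is enough. It describes evaluating effects on several sets of indices, and a statement confined to one outcome, such as handgrip strength, keeps its own 5% error rate. The inflation applies to a claim that the programme works because something was significant. That is correct, and a reader who infers that the plan declares efficacy on any single result goes too far: section 2.5 contains no decision rule in either direction. What remains is that the rule is undefined and selective emphasis is not prevented.

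Other stronger readings also lack support:

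- **A false positive is more likely than not.** With 12 outcomes and one test each, every figure is below one half. Passing one half requires counting further comparisons, or 14 or more independent variables.
- **Sidak certainly adjusts nothing.** That holds only if the comparisons are made within factor levels, which is plausible but not stated.
- **The sample size is wrong.** It is reproducible for one outcome, given ρ = 0.5.
- **Adjusting all 12 outcomes is unaffordable.** The power loss depends on an unstated correlation and ranges from severe to slight.
- **Body fat has to be primary.** It is listed first, but eligibility is set by BMI and the documents express no preference.

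Figure 1 is not reproduced in the text available. Its caption describes only the measurements taken before and after, so it is unlikely to contain a hierarchy.

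**Conclusion.** The point holds. No outcome is primary, at least 12 share one efficacy objective, all are tested at 0.05 without control across outcomes, and the power statement belongs to no named hypothesis. On the narrowest count, one interaction test for each of 12 outcomes, the chance of at least one false positive with no true effect is about 23% to 46%, roughly 5 to 9 times the nominal 5%. The range rests on assumed inter-outcome correlations from 0.7 down to 0, since the documents give none. The additional tests in section 2.5 push it higher by an amount that depends on how the pairwise comparisons are carried out. This should be settled before 6-month data exist, because it determines what the trial can claim.

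**What to change.** Before any 6-month measurement is taken, amend sections 1 and 2.5 to do the following:

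1. Name one primary outcome, defined by variable and unit. The choice is the investigators'; body fat is only one candidate.
2. Name one primary between-group test at two-sided 0.05. The planned group-by-time interaction is sufficient. Whether to adjust for baseline instead is a separate matter and is not needed for this repair.
3. Tie the power statement to that outcome and state the assumed pre-post correlation (0.5 reproduces N = 32). If a different value is more plausible for the chosen outcome, rerun the calculation.
4. Label all other outcomes secondary. Either control them by Holm or Benjamini-Hochberg within the health, functional and dietary families, or report them as estimates with 95% confidence intervals and no efficacy claim.
5. State which comparisons the Sidak step covers, and that the percentage-change t-tests are supportive.

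The cost is protocol and SAP wording. With one primary test the error rate is 5% and N stays at 32 if ρ = 0.5 is retained; a different correlation would change N. The downside is that the non-primary outcomes lose stand-alone confirmatory status.
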